1.0 SCHEMA

2.0 BACKGROUND

Liver malignancies, especially hepatocellular carcinoma (HCC), often arise in patients with cirrhosis, who exhibit significant variability in their liver function. The primary methods of assessing the severity of cirrhosis are clinical scoring systems such as the Child-Turcotte-Pugh (CTP) score or the Modified End-Stage Liver Disease (MELD) score. The Barcelona Clinic Liver Cancer (BCLC) staging, Cancer of the Liver Italian Program (CLIP) score, and the newest albumin-bilirubin (ALBI) grade have been proposed as alternative ways to assess the severity of liver dysfunction. Patients with liver tumors who need radiation may not be diagnosed with cirrhosis but may have significant alteration in their liver function due to prior chemotherapy or other local therapy. The gold standard lab test for global liver function evaluation is indocyanine green retention at 15 minutes (ICG15). However, one of the most clinically important limitations of all these tests is the lack of information that they provide regarding regional variations in hepatic function within the liver of an individual patient, which are increasingly well described. Such regional variability can have important implications for radiation treatment (RT) planning, delivery, and outcome assessment in patients with liver cancer. Recently, visualizing regional differences in hepatic function has become possible with the development of imaging techniques using technetium-99m (Tc99m) hepatobiliary iminodiacetic acid (HIDA) scans, Tc99m galactosyl human serum albumin (GSA) scans, dynamic contrast enhanced (DCE) computed tomography (CT), DCE magnetic resonance imaging (MRI), and functional MRIs (fMRIs) using contrast agents such as Eovist. Theragnostic imaging is the application of quantitative information from imaging studies to guide therapeutic interventions. These technologies therefore may have important applications in RT for liver cancer as they can provide a “road map” for how to design radiation plans to avoid functioning liver.

Hepatobiliary tumors globally are the fifth-most common cause of cancer and the second leading cause of cancer death.[1] In the United States in 2015, there are expected to be 46,570 hepatobiliary malignancies with 28,250 deaths. Hepatocellular carcinoma (HCC) is the most common type of hepatobiliary tumor. The primary risk factors for HCC are chronic hepatitis B and C infections, although cirrhosis of any cause increases the risk. The rising incidence of hepatitis C has caused HCC to become one of the fastest-growing cancers in terms of incidence and death in North America.[1] Surgical resection and liver transplantation offer the best outcomes, with 5-year overall survival (OS) rates of 50-85%.[2-5] Unfortunately, many HCC patients are not candidates for surgical resection due to the presence of locally advanced disease or medical comorbidities. In addition, only select patients with early stage HCC (tumors <5 cm) are candidates for liver transplantation.[6] For patients who are not surgical candidates or who refuse surgery, a variety of nonsurgical treatment modalities are available, including radiofrequency ablation (RFA), transarterial chemoembolization (TACE), radioembolization (Y-90), chemotherapy (primarily sorafenib-based), and radiation therapy (RT). TACE, RFA, and RT can be used as “bridging” therapies to prevent disease progression in patients awaiting transplantation. However, to date, there have been no randomized trials comparing these modalities. A discussion at a multidisciplinary tumor board where physicians from each respective specialty of surgery, interventional radiology, radiation oncology, hepatology, and radiology often determines which modality is pursued. Similarly, the other hepatobiliary tumors, namely cholangiocarcinoma and gallbladder cancer, are primarily treated with surgery if possible. An additional indication for focal liver radiation therapy exists in patients with oligometastases from certain primary malignancies, such as colon, lung, or breast cancer.

Historically, the use of radiation in cancers of the liver was limited due to the risk of radiation-induced liver disease (RILD), which is characterized by anicteric ascites and elevated transaminase levels. No standard method of reversing RILD is known, and it can lead to fatal liver failure. The risk

of RILD is best correlated with mean liver dose, reflecting the presence of a strong dose-volume correlation with the risk of RILD. Additionally, the liver is considered a “parallel” organ that can be treated with ablative radiation doses as long as adequate reserve tissue is maintained.[7, 8] Therefore, radiation therapy (RT) has gained an increasing role in the treatment of liver tumors given the development of highly conformal methods of delivery, including intensity modulated radiation therapy (IMRT), proton therapy, and stereotactic body radiation therapy (SBRT). Unlike conventionally fractionated radiotherapy, where a treatment course is administered daily over the course of a few weeks, SBRT delivers highly focused radiation with sharp dose gradients over a shorter treatment course, usually 1 to 6 fractions. Liver SBRT has been established as a safe and effective option in both liver metastases and HCC.[9-12] Rusthoven et al treated patients with SBRT (54 Gy in 3 fractions) for liver metastases and found a 2-year local control (LC) rate of 93% and no grade 3 hematologic or hepatic toxicity.[9] A phase I/II trial in HCC patients from Indiana University reported 2-year LC rates of 90%.[10] The largest prospective phase I/II trial in HCC patients from Princess Margaret reported a 2-year LC rate of 74%, but 55% of these patients had vascular invasion, which is a poor prognostic factor.[12]

Significant variability in liver function is present in the population of patients with liver tumors and cirrhosis. Different models for grading the severity of cirrhosis are available, including the Child-Turcotte-Pugh (CTP) and Model for End-Stage Liver Disease (MELD) score. To date, CTP score has been the preferred scoring system in evaluating patients for consideration of SBRT. There are other staging and prognostic scores for patients with HCC including the AJCC stage, BCLC stage, CLIP score, and ALIBI score. The CTP score is based on the levels of bilirubin, albumin, and PT/INR; it also incorporates a subjective grading system for ascites and encephalopathy. The range of scores is 5 to 15, with scores 5-6 classified as CTP A, 7-9 CTP B, and 10-15 CTP C.[13] The risk of side effects has been suggested to increase with higher CTP scores. In the study by Choi et al, 75% of their patients had CTP A disease, and there were no grade 3 toxicities reported in their trial. [11] One-third of patients in the phase I/II trial at Indiana University experienced grade 3 hematologic or hepatic toxicity, although 17 out of 21 of those patients had pre-treatment grade 2 dysfunction in that category. In addition, there were 4 patients who had progressive liver dysfunction, 2 of whom went on to liver transplantation and the other 2 who died as a result of liver failure. All 4 of these patients had CTP \geq B8, and 2 of those patients were treated with 42 Gy in 3 fractions, which was concluded to be unsafe in CTP B patients.[10]

In addition to baseline liver dysfunction, many of the patients who are referred for liver SBRT have had prior therapies such as surgical resection, chemotherapy, RFA, TACE, or conventional radiotherapy, which can adversely affect liver function. A recent retrospective study from Michigan comparing their institutional experience of SBRT with RFA found that patients who were treated with SBRT were more likely to have received prior liver-directed therapies with a median of 2 treatments in SBRT patients compared to 0 in RFA patients.[14]

We propose that, by assessing global and regional liver function before and after liver radiation, we will be able to identify correlations between radiation dose to the normal liver and the risk of RILD. An improved understanding of the relationship between radiation dose and the risk of liver toxicity will permit assessment of the risk of RILD before RT, thereby improving the safety profile of liver RT, allowing appropriate patient selection and dose determination, and establishing a standard approach for theragnostically planned radiation therapy.

Theragnostic imaging is a term coined by Soren Bentzen to describe the application of quantitative information from biomedical imaging to guide therapy.[15] He proposes a technique which he calls “dose-painting by numbers,” suggesting that imaging techniques that can visualize areas that may

potentially be radioresistant such as hypoxic areas can serve as a map on which dose can be escalated to in a voxel to voxel manner.[16] This protocol would apply the technique of theragnostic imaging in a new way. We propose the idea of “dose-erasing by numbers” to optimize our radiation dose away from areas of functional liver. In taking the regional variation of liver function into account, we propose that radiation plans designed in such a way that maximizes safety by minimizing risk of toxicity. This protocol will aim to determine the clinical feasibility of applying such a technique in the clinic.

Currently, standard constraints for liver SBRT planning stipulate that 700 cc of “uninvolved liver”, i.e., the volume of liver minus the gross tumor volume (GTV), should receive <15 Gy. This constraint is derived from a phase I study conducted at the University of Colorado (which itself was based on surgical data showing that 75-80% of the liver can be safely resected).[9, 17] Since 25% of the assumed average liver volume of 2000 cc is 500 cc, 700 cc was used as a conservative limit. The basis for 15 Gy was that its BED is 40 Gy₃ which is less than the whole liver tolerance of 49.5 Gy₃ as determined from an early RTOG dose escalation study of whole liver RT.[18] The current constraint does not take into account the functional residual capacity of the untreated liver. However, information about regional variations in liver function could help to evaluate the safety of RT in patients who are borderline candidates for liver RT based on their liver function. In this protocol, we will meet the standard physical constraints but plan to increase safety further by attempting to decrease dose to functional areas.

The indocyanine green (ICG) retention study is presently the gold standard for assessing liver function, but this study only provides information about global liver function.[19] An ICG retention at 15 minutes (ICG15) of less than 14% has historically been used as a cutoff to select patients for major hepatectomy, but subsequent trials have shown that well-selected patients with ICG15 values above this cutoff had similar outcomes as those with lower ICG15 values[20, 21] According to the 2016 NCCN hepatobiliary guidelines, ICG15 is widely used in Asia but not in Western countries. Two studies from the University of Michigan reported baseline ICG values in patients’ pre-treatment. They reported ICG clearance as ICG half-life, whereas the surgical data looks at ICG retention at 15 minutes (ICG15). In a total of 29 patients, the values ranged from 3.75 minutes to 14.5 minutes, which would correlate with an expected ICG15 of 6.25% to 48.8%. In this study, 14 of 29 (48.3%) of patients would have had a ICG value >14%. Clearly, the patients undergoing radiation therapy for liver tumors can have a large variation in their liver function. Having more data as to what functional residual capacity correlates with the ability to safely deliver radiation therapy would be beneficial.

Alternative radiographic assessments of regional liver function, including the hepatobiliary Tc99m-iminodiacetic acid (HIDA) scan, dynamic contrast enhanced (DCE) CT, DCE MRI, and fMRI with contrast agents such as Eovist are being explored. These have been validated by comparison to ICG to demonstrate their correlation with liver function.[22-26] Unfortunately, direct comparisons of these modalities are complicated by a lack of uniformity in reporting of imaging data. In addition, it is unknown how to best incorporate information derived from these studies in radiation treatment planning.

HIDA scans have been evaluated in both the surgery and radiation therapy settings. In the surgical setting, HIDA scans have been used in an effort to identify patients who are at higher risk for postoperative complications including liver failure and death. Much of the pioneering work for the use of HIDA scans in pre-operative evaluation has been done in the Netherlands. A Dutch study reported that HIDA scans were effective in predicting postoperative morbidity and mortality; this report showed that a 2.5%/min/m² of body surface area (BSA) in the residual (non-resected) liver was the threshold value that predicted for postoperative liver failure. Patients with a FRL uptake above

2.5%/min/m² of BSA had a 3% chance of developing postoperative liver failure and liver-failure related mortality, whereas patients with FRL uptake below 2.5%/min/m² had a 56% chance of postoperative liver failure. A recent update to these data gives 2.7%/min/m² as the safe cutoff. This study also demonstrated a weak but positive correlation ($r=0.61$) between HIDA scan values for predicting volume regeneration at 3 months post-resection.[27] The University of Michigan has also evaluated the potential use of HIDA in radiation treatment planning. They used a different parameter, the hepatic ejection fraction (HEF), and validated it with ICG. They obtained HIDA scans pre-treatment, during treatment (after 50-60% of the planned dose had been delivered), and 1 month post treatment. They derived models which predicted HEF-dose response and found that the model which incorporated the HIDA scan during treatment improved their predictive power given variation in individual radiation sensitivity, suggesting that adaptive radiation planning in order to direct dose through worse functioning portions of the liver may improve the safety of radiation delivery.[24] The study from Michigan provides further validation of the HIDA scan as a reasonable surrogate for liver function.

HIDA scans are a relatively inexpensive and simple imaging technique. In patients undergoing liver resection, preoperative HIDA threshold values of $>2.7\%$ uptake/min/m² have been shown to correlate with a decreased risk of postoperative liver failure. However, it is unknown whether similar HIDA threshold values can be used to determine the safety of radiation therapy in patients who are candidates for treatment with this modality, although some preliminary investigations of HIDA scans to measure post-RT liver function have been reported. Further work is needed to identify thresholds below which a given patient may be at high risk for developing radiation-induced liver disease (RILD).

techniques in evaluating functional residual liver volume. These studies also provide preliminary image-based information about the dose-response relationship of normal liver tissue. However, these studies were limited by the heterogeneous patient population and the short follow-up period (only one month post treatment). The HIDA parameter of HEF which was studied at Michigan has not been prospectively evaluated as a predictor of worse clinical outcomes, unlike the % uptake/min/m² parameter, which is how HIDA scans are reported at our institution. Finally, and perhaps most importantly, the prior HIDA studies provide no information on the correlation of imaging findings with post-treatment liver function tests, CTP score, or MELD. An exploratory analysis to determine the correlation of functional imaging to liver regeneration and the standard scoring systems such as CTP or MELD is planned.

A Japanese study evaluated different MRI parameters from DCE MRI and their correlation with Tc99m galactosyl human serum albumin (GSA) scans, with validation using ICG. Interestingly, they also correlated the different functional imaging studies with CTP score, a useful clinical parameter which none of the University of Michigan papers evaluated. GSA is a radiotracer specific for hepatocytes, binding to the asialoglycoprotein (ASGP) receptor on the sinusoidal and lateral surfaces of hepatocytes. It is similar to the HIDA scan and is widely used in Asia, but GSA is currently not FDA approved in the United States. Typical parameters evaluated through GSA are the ratio of GSA radioactivity of the liver to heart-plus-liver (LHL15) and percent of cumulative uptake from 15-16 minutes (LU15). They found that the intracellular contrast uptake ratio (UR) from DCE MRI had correlations with the GSA scan parameters LHL15, LU15, CTP score, and ICG15. The weak correlation of UR with fibrosis trended toward significance. A different MRI parameter, the extracellular volume (Ve), correlated with fibrosis, but was not found to have significant correlation to the GSA parameters, ICG15, or CTP score. The authors concluded that neither MRI nor GSA was the ‘correct’ method, and more work is needed to investigate what the most sensitive marker for liver function is.[30] A secondary aim of the paper would be to correlate HIDA scan parameters with CTP score as well as with different parameters from other imaging techniques such as diffusion-weighted MRI. We also plan to analyze if there is a correlation between these parameters and the regenerative capacity of the liver.

In order to quantitate the dosimetric improvements that theragnostically planned radiation will offer, we plan to analyze the plans using a functional dose-volume histogram. Conventional dose-volume histograms assume that a given organ is homogeneously functioning and thus spatial and functional information is lost. Functional dose-volume histograms were proposed as a technique to analyze radiation plans in the early 1990s by Lawrence Marks of Duke and also in the Netherlands.[31, 32] Since then, most of the work with regards to the use of functional DVH analysis has been done in lung cancer with single photon emission CT (SPECT) using ⁹⁹Tc-labeled macroaggregated albumin (MAA) perfusion imaging.[33, 34] A group in France described a technique of using the SPECT scan to design an IMRT plan that was optimized to reduce the V20 to functional lung. Their definition of functional lung was defined as 60% of the maximum uptake of the SPECT scan.[35] This definition of functional lung, while utilitarian, does not account for the heterogeneity that can exist from one patient to another as there is no standard “global lung function” upon which different patients’ scans can be normalized. The HIDA scan technique provides a global liver function from which we can scale the regional function to know more quantitatively rather than qualitatively how a given area of liver is functioning. The only use of functional DVH use for analysis of liver radiation plans comes from a study in Japan where they were studying the use of GSA scans in liver radiation planning. They acknowledged the difficulty of defining a universal liver function. They defined functional liver as uptake of liver greater than the HCC, while dysfunctional liver was up take similar to that of HCC. Using this definition they found that if the V20 to functional liver was <20% was associated with a <20% risk of deterioration in CTP score.[36] These studies demonstrate the

feasibility of optimizing a radiation plan based on an individual patient's functional map generated from an image. The difficulty interpreting these studies is that a global organ function has not been clearly defined in a reproducible manner. For example, the uptake of a HCC can vary from one patient to another. Our technique of HIDA scan interpretation gives a reliable global liver function from which a given percentage of counts within the scan can be scaled to a quantitative value which can be compared from patient to patient.

3.0 RATIONALE

The goal of the present study is to evaluate whether theragnostically planned liver radiation through the addition of a HIDA scan can reduce the dose of radiation to functional liver as compared to conventionally planned liver radiation without compromising target coverage or tumor control. We believe that a better understanding of the application of HIDA scans in patients undergoing radiation therapy will assist in patient selection and may permit further customization of RT plans to minimize post-treatment hepatotoxicity.

4.0 OBJECTIVES

4.1 Primary Objective

1. To assess whether theragnostically planned liver radiation through the use of a HIDA scan can reduce the dose of radiation to functional liver as compared to conventionally planned liver radiation.

4.2 Secondary Objectives

1. To assess the rate at which the theragnostically planned radiation plan is chosen as the actual treatment plan instead of the conventionally planned radiation plan.
2. To collect data regarding local control (LC), progression free survival (PFS), overall survival (OS), time to transplant (TT), distant liver failure, and salvage therapy in patients undergoing functional image-guided planning for liver SBRT. To document patterns of failure so that local failure versus distant liver failure can be accounted for.
3. To assess treatment toxicity.

4.3 Exploratory Objectives

1. To identify correlations between radiation dose to the normal liver and the risk of RILD.
2. To determine the feasibility of incorporating functional liver MRI (i.e., fMRI which will be done via MRI with Eovist contrast) into theragnostic liver radiotherapy planning.
3. To assess the rate of significant change in HIDA scans midway through treatment.

4.4 Primary Endpoint

1. The functional reserve of liver will be calculated for both a plan that takes the HIDA scan into account and a plan that does not take this into account. The functional reserve will be calculated by (number of counts outside 15 Gy isodose line / total number of counts within the liver) * global liver function.

4.5 Secondary Endpoints

1. The rate at which the theragnostically planned radiation plan is chosen as the actual treatment plan rather than the conventionally planned radiation plan.

2. LC, PFS, OS, time to transplant, distant liver failure, and time until salvage treatment
3. Post treatment changes in liver function tests and CTP score. We plan to document the rate of decline of CTP class as well as the rate of any grade of hepatic toxicities.

4.6 Exploratory Endpoints

1. Correlations between radiation dose to the normal liver and the risk of RILD.
2. Correlation between the quantitative data from fMRI and HIDA scan values. Also, a preliminary exploration of the doses at which changes in fMRI are seen.
3. The rate at which the HIDA changed enough such that the radiation plan could have been adapted to decrease the amount of functional liver receiving >15 Gy.

5.0 ELIGIBILITY CRITERIA

5.1 Inclusion Criteria

1. Subjects must be ≥ 18 years of age at the time of signing informed consent
2. Diagnosis of primary liver malignancy (including hepatocellular carcinoma [HCC] or cholangiocarcinoma) or liver metastasis from any primary solid tumor site by characteristic imaging findings on CT or MRI, clinical presentation, and/or pathologic confirmation of diagnosis. Subjects with other current or prior malignancies are eligible for this study.
3. Patients with liver metastases must have at least one of the following clinical factors that may affect liver function:
 - a. History of liver resection (at any time)
 - b. History of cirrhosis (any cause), fatty liver disease, or hepatic insufficiency due to any cause
 - c. Prior radiation to the upper abdomen including radioembolization
4. ECOG (Zubrod) Performance Status 0-2.
5. Subjects must have a Child-Turcotte-Pugh (CTP) score ≤ 7 to be eligible.
6. Patients who have been previously treated with non-SBRT liver directed therapies may be enrolled on study. At least 3 months must have elapsed between the most recent liver-directed therapy and study entry.
7. Ability to provide written informed consent and HIPAA authorization
8. Subjects with an allergy to contrast agents may be enrolled at the treating physician's discretion with appropriate pre-treatment and symptom management.

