11.0 TOXICITIES TO BE MONITORED/DOSAGE MODIFICATIONS

All subjects will have laboratory evaluation prior to initiation of treatment. This includes CBC with differential, platelets, CMP, and INR.. Radiation treatment will be suspended in subjects who develop new ascites (as indicated by abdominal ultrasound, CT scan, or physical exam) or encephalopathy. If the patient's clinical status is borderline and the treating physician determines a treatment break is necessary, re-evaluation for further treatment can occur 1-2 days later.

	CTP-A	CTP-B7
Total Bilirubin	<3	<4
Albumin	>2.5	>2.5
INR	<1.5X upper normal	PT > 6 seconds above normal
ANC	>1000	>1000
Platelets	>50,000	>50,000
Hgb	>9	>9
Ascites	none	none
Encephalopathy	none	none

The subject will be seen at least once weekly during treatment for assessment of side effects. The most current version of Common Terminology Criteria for Adverse Events (CTCAE) will be used for grading toxicity.

For the purposes of this study, we will monitor the following:

- Labs: AST, ALT, Alkaline phosphatase, bilirubin, INR, platelets, albumin, lymphocytes, sodium
- Hepatobiliary disorders: hepatic failure, hepatic hemorrhage, hepatic necrosis, hepatic pain, perforation of bile duct, portal hypertension, portal vein thrombosis, bile duct stenosis, biliary fistula, cholecystitis, gallbladder fistula
- Gastrointestinal disorders: ascites, duodenal hemorrhage, duodenal obstruction, duodenal perforation, duodenal stenosis, duodenal ulcer, gastric necrosis, gastric perforation, gastric stenosis, gastric ulcer
- Nervous system disorders: encephalopathy
- Musculoskeletal and connective tissue disorders: chestwall pain
- Renal and urinary disorders: acute kidney injury

A copy of the most current CTCAE version is available at <http://ctep.cancer.gov/reporting/>

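### For an eligible subject with stable baseline ascites or encephalopathy, the CTP entry rule, the section 11 suspension text and the section 11 table do not agree

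*Combined protocol and SAP*

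**What the plan says.** **Entry.** Section 5.1, item 5: "Subjects must have a Child-Turcotte-Pugh (CTP) score ≤ 7 to be eligible". This limits the total only. No item in 5.1 or 5.2 limits a single component or names ascites or encephalopathy.

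**The score.** Section 2.0 lists bilirubin, albumin and PT/INR, and adds that "it also incorporates a subjective grading system for ascites and encephalopathy". It continues: "The range of scores is 5 to 15, with scores 5-6 classified as CTP A, 7-9 CTP B, and 10-15 CTP C".

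**Treatment.** The section 11.0 text reads: "Radiation treatment will be suspended in subjects who develop new ascites (as indicated by abdominal ultrasound, CT scan, or physical exam) or encephalopathy". The table below it has columns for CTP-A and CTP-B7, with the rows "Ascites none none" and "Encephalopathy none none". It has no caption or lead-in that says what follows when a row is not met.

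**RILD.** The only description is in section 2.0: "which is characterized by anicteric ascites and elevated transaminase levels". RILD is an exploratory endpoint (4.6), to be examined with graphs and descriptive statistics (13.8).

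**Toxicity.** Section 4.5 plans the rate of hepatic toxicity of any grade and the rate of decline in CTP class. Section 13.7 limits treatment-emergent events to those that begin or get worse while the subject is on treatment.

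**Analysis sets.** Sections 13.3.2 and 13.3.3 both require that the subject has been irradiated at least once.

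**The concern.** A subject with long-standing, stable ascites meets three rules that give different messages. Section 5.1 admits the subject. The section 11 text does not suspend treatment, because nothing has developed. The section 11 table has a row that the subject does not satisfy.

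Two things depend on how a site resolves this. The first is who is irradiated, and so who is in the analysis sets. A subject held back before the first fraction has already been registered and planned twice, but is in neither set. The second is how liver toxicity is counted. A subject who is treated may begin with the sign that forms part of the RILD description, and the plan has no baseline-adjusted definition of RILD. Ascites present throughout could be counted as RILD, or true worsening could be put down to the baseline condition.

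**Working it through.** **1. The plan's own figure.** Section 13.4 gives an 87% chance of at least 3 responders among 15 when the true rate is 30%. The exact binomial tail, 1 − Σ(k=0 to 2) C(15,k)·0.3^k·0.7^(15−k), is 0.873. The other entries also reproduce: 0.184, 0.602, 0.764, 0.973 and 0.996 at true rates 0.1, 0.2, 0.25, 0.4 and 0.5. None of these uses the CTP rule.

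**2. Can an eligible subject have either sign?** Section 2.0 names five components and a range of 5 to 15. That implies 1 to 3 points each (5 × 1 = 5; 5 × 3 = 15). This is an inference, since the documents print no point table.
- Ascites at 2 points, the other four at 1: 2 + 4 = 6, CTP A6, eligible.
- Ascites at 3 points, the other four at 1: 3 + 4 = 7, CTP B7, eligible.
- The same sums hold for encephalopathy.

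Counting the component patterns with a total of 7 or less:

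| Total | Patterns | With ascites or encephalopathy above the lowest grade |
|---|---|---|
| 5 | 1 | 0 |
| 6 | 5 (one component at 2) | 2 |
| 7 | 5 (one at 3) + C(5,2) = 10 (two at 2) = 15 | 2 + (10 − C(3,2)) = 2 + 7 = 9 |
| All | 21 | 11 |

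This shows that admission is possible in both classes. It says nothing about how often it happens.

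**3. The three rules side by side.**

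| Subject | 5.1 item 5 | Section 11 text | Section 11 table |
|---|---|---|---|
| Neither sign, total ≤ 7 | Eligible | No suspension | Both rows met |
| Stable baseline ascites, total ≤ 7 | Eligible | No suspension (nothing has developed) | Ascites row not met |
| Ascites arising during treatment | Was eligible | Suspend | Ascites row not met |

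The rules conflict only in the middle row. Stable baseline encephalopathy falls in the same position.

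**4. Consequence under each reading of the table.**
- *Start condition:* no dose is given, so the subject is outside the sets in 13.3.2 and 13.3.3 and uses up part of the margin of 20 − 15 = 5 in section 13.4.
- *Not a start condition:* the subject is treated with the ascites part of the RILD description already present.

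**5. How many?** The documents give no prevalence. As an assumption only, if 5% to 30% of enrolled subjects had either sign at baseline, that would be 20 × 0.05 = 1 to 20 × 0.30 = 6 subjects.

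**The case against.** The best defence is that the table can be read with the sentence above it, as an on-treatment monitoring list under a heading about toxicities and dose modification. On that reading stable baseline ascites triggers nothing. This stands as a possible reading. The document does not state it, however, and as printed the table does not separate new from existing signs.

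The second defence is that the plan already handles much of the toxicity problem. Section 13.7 counts only adverse events that begin or worsen on treatment, and section 4.5 looks at changes in liver function tests and CTP score. This stands for the adverse-event tables. It does not reach RILD, which has no operational definition. The CTP safeguard is partial: the section 10.0 calendar marks the score at baseline and midway only, and section 8.4 lists only laboratory tests at the 30-day visit.

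A reader might infer more than the documents support:
- *That eligible subjects breach the treatment table on day one.* This holds only if the table is a condition for starting or continuing, which is nowhere stated, and only for subjects who have either sign.
- *That such subjects cannot be assessed for RILD.* AST, ALT, alkaline phosphatase and bilirubin are monitored (section 11.0), and worsening ascites is still observable. Encephalopathy is not part of the RILD description at all.
- *That about half of subjects are affected, because 11 of 21 patterns (52%) include a sign.* These are unweighted arithmetic combinations, not patients. The requirement for written consent (5.1, item 7) may also screen out some encephalopathy.
- *That toxicity rates would move by 10 to 20 percentage points.* That is 2/20 to 3/15. It assumes both the number of affected subjects and that every one is misclassified, and the documents support neither.

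**Conclusion.** The concern holds as an internal inconsistency of limited reach. The entry rule can admit subjects with ascites or encephalopathy as A6 or B7, given the inference of 1 to 3 points per component. For those who are stable, the entry rule, the suspension text and the table give no single answer. What is at stake is whether a few eligible subjects are irradiated and analysed, and whether baseline ascites is kept apart from toxicity in the exploratory RILD analysis and the hepatic-toxicity rate.

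The number affected is unknown; the 1 to 6 of 20 shown above rests wholly on an assumed prevalence. The primary endpoint compares two plans within the same subject from HIDA counts (section 4.4), so that comparison is unaffected. So is the 87%, which depends only on 15 evaluable subjects and the assumed true rate. The point merits correction, but it does not threaten the main question.

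**What to change.** 1. In section 11.0, state what the table is for (starting, continuing or monitoring treatment) and reconcile it with 5.1 item 5 and the suspension text, so that one rule applies to a subject with a baseline sign. The content of that rule is for the clinical team.
2. In sections 13.7 and 13.8, state that ascites and encephalopathy enter the hepatic-toxicity rate, and ascites enters any RILD classification, as change from the baseline component score. This matches the approach 13.7 already takes to treatment-emergent events.
3. Keep the baseline ascites and encephalopathy component points in the database, not only the CTP total. Section 8.1 already requires the score. Grade both signs at follow-up from the physical examination and toxicity assessment already scheduled in 8.5, so that there is a later value to compare.

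The cost is minor wording, two or more retained data fields and a little analysis work. No new visit or test is needed, and the sample size does not change.
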